6.3 Pharmacokinetics Variables

Plasma concentration data of ASP2215 will be used in pharmacokinetic analysis.

6.4 Other Variables

Duration of exposure

Duration of exposure to each component of a study drug will be calculated in days, using the following formula:

Last date of exposure – First dose date + 1 – (on-study HSCT period for subjects undergo on-study HSCT)

For ASP2215, last date of exposure = last dose date of ASP2215

For chemotherapy, last date of exposure = (initial dose date of the last cycle +28-1) or death date if death occur within last cycle

When the start or stop date is missing, then the exposure will be treated as missing.

Duration of exposure for a chemotherapy regimen, i.e. MEC and FLG-IDA, will be the maximum (duration of exposure of all treatment components).

When the last date of exposure is beyond cutoff date, the cutoff date will be used as the last date of exposure.

Number of dosing days

Number of days with non-zero dosing.

Number of cycles

Number of cycles for each component of study drug refers to total number of cycles with non-zero dosing in the cycle.

Number of cycles for a chemotherapy regimen refers to total number of cycles with non-zero dosing of any treatment component in the cycle.

• Cumulative dose (dose unit)

Cumulative dose will be calculated using the following formula for each type of study drug:

- ASP2215: Sum of [(stop date start date + 1) * dose captured on dosing CRF] across all records
- LoDAC: Sum of (number of dose taken * 20mg) across all records and all cycles.
 If number of dose take is "unknown", it will be treated as missing.
- Azacitidine: Sum of (number of dose taken * actual delivered dose captured on dosing CRF) across all records and all cycles. If number of dose taken is "unknown", it will be treated as missing.

 Each component of MEC and FLAG-IDA: Sum of (actual delivered dose captured on dosing CRF) across the days when study drug was administered. If answer to "entire infusion administered" is No, actual delivered dose will be treated as missing.

• Average daily dose (dose unit/days)

Cumulative dose (dose unit)

Number of dosing days (days)

Dose intensity

Dose intensity will be calculated in mg/day for ASP2215 as:

Cumulative dose (mg)

Duration of exposure (days)

Dose intensity will be calculated in dose unit/cycle for chemotherapy as:

Cumulative dose (dose unit)

----- x 28 (days/cycle)

Duration of exposure (days)

• Relative dose intensity

Relative dose intensity for ASP2215 will be calculated as:

Dose intensity (mg/day)

-----x 100%

120 (mg/day)

Relative dose intensity for each component of chemotherapy will be calculated as:

Dose intensity (dose unit/cycle)

----- x 100%

Planned dose intensity (dose unit/cycle)

Where planned dose intensity (dose unit/cycle) will be calculated based on protocol specified dose:

o LoDAC: 40 mg/day * 10 days/cycle

 \circ Azacitidine: 75 mg/m²/day * BSA * 7 days/cycle

o MEC

Mitoxantrone: 8 mg/m²/day * BSA * 5 days/cycle Etoposide: 100 mg/m²/day * BSA * 5 days/cycle Cytarabine: 1000 mg/m²/day * BSA * 5 days/cycle

o FLAG-IDA

G-CSF: 300 μ g/m²/day * BSA * 5 days/cycle Fludarabine: 30 mg/m²/day * BSA * 5 days/cycle Cytarabine: 2000 mg/m²/day * BSA * 5 days/cycle Idarubicin: 10 mg/m²/day * BSA* 3 days/cycle

Average of BSA for all dosed cycles will be used in the calculation of planned dose intensity.

- Relative dose intensity for a chemotherapy regimen will be the average of relative dose intensity of all treatment components.
- Duration of AML

Duration of AML will be calculated in days using the following formula:

(Randomization date – date of initial diagnosis of AML) + 1

Partial date of initial diagnosis of AML will be imputed per Section 7.11.1.

- Previous and concomitant medication
 - Previous medication is defined as medication with at least one dose taken before the date of the first dose of study drug (exclusive).
 - Concomitant medication is defined as medication with at least one dose taken between the date of first dose (inclusive) and the date of last dose (inclusive) of study drug.

For subjects that undergo HSCT without leaving the study and plan to resume ASP2215 treatment after HSCT, concomitant medication is defined as medication with at least one dose taken between the date of first dose (inclusive) and the date of last dose (inclusive) before pre-HSCT visit, or between resumption of ASP2215 (inclusive) and the date of last dose (inclusive).

- Prior Use of FLT3 inhibitor
 - Prior Use of FLT3 inhibitor is defined as "Yes" if subjects received prior AML therapy of Midostaurin, Sorafenib or Quizartinib.
- Previous and concomitant transfusion
 - Previous transfusion is defined as transfusion received before the date of first dose of study drug, i.e. transfusion completed before the date of first dose (exclusive).
 - Concomitant transfusion is defined as transfusion received between the date of first dose (inclusive) and the date of last dose (inclusive) of study drug.

For subjects that undergo HSCT without leaving the study and plan to resume ASP2215 treatment after HSCT, concomitant transfusion is defined as transfusion received between the date of first dose (inclusive) and the date of last dose (inclusive) before pre-HSCT visit, or between resumption of ASP2215 (inclusive) and the date of last dose (inclusive).

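### SAP section 6.4 does not fix the exposure window for MEC and FLAG-IDA components, so leaving a component out of a whole cycle can leave relative dose intensity at 100%

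*SAP*

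**What the plan says.** Section 6.4 sets out the calculation in stages.

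- Duration is defined for each component ("Duration of exposure to each component of a study drug will be calculated in days, using the following formula") as "Last date of exposure – First dose date + 1 – (on-study HSCT period for subjects undergo on-study HSCT".
- The end date is: "For chemotherapy, last date of exposure = (initial dose date of the last cycle +28-1) or death date if death occur within last cycle". Whose last cycle is meant is not stated.
- For MEC and FLAG-IDA, the regimen's duration "will be the maximum (duration of exposure of all treatment components".
- "When the start or stop date is missing, then the exposure will be treated as missing".
- Cycles are counted separately for components and regimens. For components: "Number of cycles for each component of study drug refers to total number of cycles with non-zero dosing in the cycle". For a regimen, a cycle counts if any component was dosed.
- "Dose intensity will be calculated in dose unit/cycle for chemotherapy as" cumulative dose divided by duration of exposure, times 28. RDI is that figure over the planned dose per cycle.
- "Relative dose intensity for a chemotherapy regimen will be the average of relative dose intensity of all treatment components".

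Section 7.3.1 plans dose intensity and RDI for each treatment regimen in the safety analysis set. It also plans cumulative amount, dosing days, number of dosing cycles and average daily dose, and counts of subjects with dose increases, decreases or interruptions. Unlike several neighbouring sections, it carries no end-of-study restriction, so the formulas remain in force in version 4.0.

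**The concern.** RDI should fall when part of the planned treatment is not given. If the denominator is the component's own span, skipping the component for a whole cycle at either end of the course takes that cycle out of both numerator and denominator. The omission then leaves no trace in RDI. If the second cycle was also late, the skipped component avoids the penalty for the delay and RDI goes up.

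A second gap concerns a component that was never given. It has no first dose date, so its duration and RDI are missing, and the section does not say whether the regimen average drops it or counts it as zero.

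At stake is how well this one summary describes delivery of the two multi-drug comparator regimens. Two programmers could also derive different values from the same data.

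**Working it through.** The SAP states no RDI value, so there is no figure to reproduce. The section 6.4 formulas were applied directly.

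**Inputs from the SAP**
- MEC has 3 components and FLAG-IDA has 4 (section 6.4).
- Planned dose per cycle, for example: mitoxantrone 8 × 5 = 40 mg/m² × BSA; idarubicin 10 × 3 = 30 mg/m² × BSA (section 6.4).
- Both regimens run for at most 2 cycles (section 2, Table 2, footnote n).

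**Assumptions**
- Cycle 2 starts on day 29, or on day 43 if delayed by 14 days.
- BSA is constant, so it cancels.
- All other doses are full.
- No death, HSCT or data cutoff falls inside the window.

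**Formula.** With planned dose per cycle P, cumulative dose k × P and duration D days, RDI = 100 × (kP / D × 28) / P = 100 × 28k / D.

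**1. Check, full dosing on schedule.** D = (29 + 27) − 1 + 1 = 56 and k = 2, so RDI = 100 × 56/56 = 100% under either definition.

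**2. One component omitted from cycle 2.** Own window: D = 28, k = 1, RDI = 100%. Common window: D = 56, RDI = 50%.
- MEC average: (100 + 100 + 100)/3 = 100% on own windows; (100 + 100 + 50)/3 = 83.3% on the common window.
- FLAG-IDA average: 100% on own windows; (100 + 100 + 100 + 50)/4 = 87.5% on the common window.

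**3. One component omitted from cycle 1 instead.** Own window: D = 56 − 29 + 1 = 28, so RDI is again 100%. The common-window results are as in step 2.

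**4. Cycle 2 delayed to day 43.** The regimen window is (43 + 27) − 1 + 1 = 70 days. Full dosing gives 100 × 56/70 = 80.0% for every component. A component given only in cycle 1 has 100% on its own window and 100 × 28/70 = 40% on the common window.

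| Cycle 2 on day 43 | Full dosing | One component omitted from cycle 2, own window | Same, common window |
|---|---|---|---|
| MEC | 80.0% | (80 + 80 + 100)/3 = 86.7% | (80 + 80 + 40)/3 = 66.7% |
| FLAG-IDA | 80.0% | (3 × 80 + 100)/4 = 85.0% | (3 × 80 + 40)/4 = 70.0% |

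**5. One component never given, cycle 2 on day 29.** Its RDI is missing. The regimen average is 100% if it is dropped. If it is counted as 0%, the average is 200/3 = 66.7% (MEC) or 300/4 = 75.0% (FLAG-IDA).

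**6. Half dose of one component in cycle 2.** k = 1.5 and D = 56, so RDI = 75% and the MEC average is (100 + 100 + 75)/3 = 91.7% under both definitions. A reduced delivered dose within a dosed cycle is detected.

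**7. The other reading: the regimen's last cycle, with the component's own first dose.** A component given only in cycle 1 has D = 56 and RDI 50%. A component first given in cycle 2 has D = 28 and RDI 100%. This reading removes the problem at the end of the course but not at the start.

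**The case against.** The component-level reading of the last cycle is inferred. Section 3.2.1 uses cycle at regimen level when it describes a second cycle of the same chemotherapy. The rule that takes a maximum over components does not settle the matter. Footnote n to Table 2 places FLAG-IDA on days 1 through 6, while section 6.4 plans 5 days (3 for idarubicin) per component. Staggered start days alone could therefore make component durations differ. The component cycle count is a separate variable and does not enter the duration formula. This stands as far as it goes: the regimen-level reading is possible. It is not stated, however, and step 7 shows that it cures only half the problem.

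A reader might infer that under-dosing of the control arm is hidden. The document does not support that. LoDAC and azacitidine are single-component regimens, so this masking cannot arise there. Reductions within a dosed cycle lower RDI. Section 7.3.1 also reports cumulative amount, dosing days and number of cycles, where an omitted cycle would show, and section 7.2.2 tabulates wrong treatment or incorrect dose as a protocol deviation (PD3).

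A reader might also infer that a component never given scores 100%. It does not: its RDI is missing, and the regimen average reaches 100% only if the missing component is dropped.

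Finally, a second cycle of MEC or FLAG-IDA is conditional, and nothing in the SAP plans for one component to be left out. The percentages are worked examples, not estimates for this trial.

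**Conclusion.** The point holds in a limited form. Section 6.4 leaves the denominator of component dose intensity open. On its natural reading, RDI does not register omission of a MEC or FLAG-IDA component from a whole cycle at the start or end of a two-cycle course. In the single-component example, the regimen figure is overstated by 100 − 83.3 = 16.7 points for MEC and 100 − 87.5 = 12.5 points for FLAG-IDA. With the assumed delay to day 43, the gap is 86.7 − 66.7 = 20.0 points for MEC and 85.0 − 70.0 = 15.0 points for FLAG-IDA, and reported RDI rises with the omission. The treatment of a never-given component in the average is unspecified.

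The effect on the reported summary depends on how often components were omitted, which the SAP does not give. Only descriptive dose intensity and RDI are involved; no endpoint, test, boundary or sample size uses them. This is a minor point, worth correcting because the correction is cheap.

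**What to change.** In section 6.4, state that for MEC and FLAG-IDA the denominator of every component's dose intensity is the regimen's exposure window: from the first dose of any component to day 28 of the regimen's last cycle, or to death if that comes earlier. Keep the existing HSCT deduction and data-cutoff rule. Define the window directly rather than borrowing the maximum over components, which would be too short if no single component was given in both cycles. Add that a planned component of the regimen that was not administered counts as 0% in the regimen average.

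The cost is a sentence or two of wording and a small programming change, with no new data. Reported RDI for the control arm may be slightly lower. If RDI was already reported in the primary clinical study report under the present wording, the end-of-study report should say which definition each report used.

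### Chemotherapy dose intensity uses a duration cut at death or cutoff, so a full single cycle followed by death on day d scores 28/d of plan

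*SAP*

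**What the plan says.** All the definitions are in SAP Section 6.4.

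- **Duration of exposure, chemotherapy.** It runs from the first dose to the 28th day of the last cycle, "or death date if death occur within last cycle". A second cut follows: "When the last date of exposure is beyond cutoff date, the cutoff date will be used as the last date of exposure".
- **Dose intensity.** "Dose intensity will be calculated in dose unit/cycle for chemotherapy as" cumulative dose divided by duration of exposure, "x 28 (days/cycle").
- **Relative dose intensity (RDI).** Dose intensity is divided by the planned dose per full cycle. The planned dose covers 5 dosing days for every MEC and FLAG-IDA component except idarubicin (for example "Mitoxantrone: 8 mg/m²/day * BSA * 5 days/cycle"), 3 for idarubicin, 7 for azacitidine ("75 mg/m²/day * BSA * 7 days/cycle") and 10 for LoDAC.
- **Regimen level.** "Relative dose intensity for a chemotherapy regimen will be the average of relative dose intensity of all treatment components".
- **Incomplete infusions, MEC and FLAG-IDA only.** If the answer to whether the entire infusion was given "is No, actual delivered dose will be treated as missing".

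Section 7.3.1 summarises dose intensity and RDI by treatment regimen on the safety analysis set. No cap or exclusion is stated. Section 1 keeps safety data in the end-of-study report, and Section 7.3.1, unlike the efficacy and baseline sections, is not marked as dropped from it.

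**The concern.** Dose intensity compares dose given with dose planned over the same span of time. Here the numerator is complete within days of the cycle's start. The planned dose in the comparison belongs to a full 28-day cycle, but the observed denominator stops at death or cutoff. The same delivered dose is spread over fewer days and scaled back up to 28.

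A patient who receives exactly the planned cycle and dies early is therefore reported as having received a multiple of plan, and one whose course was cut short by death can also appear overdosed. Means and maxima of dose intensity and RDI in the chemotherapy regimens are distorted upward. RDI for ASP2215 does not have this problem: dosing is daily, the denominator ends at the last dose, and the reference is 120 mg per day. The two arms' RDI values are therefore not on the same footing.

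**Working it through.** The SAP states no RDI value to reproduce, so the check applies its own formulas.

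**Inputs (Section 6.4).** Let g be the number of planned-size daily doses given, p the planned dosing days per cycle (5, 7 or 10; 3 for idarubicin) and D the duration of exposure in days. The daily dose and body surface area cancel, taking body surface area as constant over cycles:

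RDI = (g / D) × 28 / p × 100%.

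**Step 1: nothing truncated.** One full 5-day cycle: (5/28) × 28/5 = 100%. Two full cycles: (10/56) × 28/5 = 100%. The formula is correct when the last cycle is left whole.

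**Step 2: one full cycle, death on day d.** Here g = p and D = d, so RDI = 28/d for any component completed by day d. A cutoff on day d has the same effect.

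| Day d | RDI |
|---|---|
| 7 | 28/7 = 400% |
| 10 | 28/10 = 280% |
| 14 | 28/14 = 200% |
| 20 | 28/20 = 140% |
| 27 | 28/27 = 104% |

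The 10-day LoDAC course cannot exceed 280% once complete.

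**Step 3: incomplete course.** Three of five doses with death on day 4: (3/4) × 28/5 = 420%. Five of ten LoDAC days with death on day 7: (5/7) × 28/10 = 200%.

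**Step 4: more than one cycle.**

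- Two full 5-day cycles, death on day 7 of cycle 2: (10/35) × 28/5 = 160%.
- The same, death on day 14 of cycle 2: (10/42) × 28/5 = 133%.
- Three full azacitidine cycles, death on day 14 of cycle 3: (21/70) × 28/7 = 120%.
- Death after day 28 of the last cycle: no effect.

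**Step 5: how often (assumption, for scale only).** Section 4 plans 123 control subjects with a 5-month median OS. If survival were exponential (month = 30.4375 days), the proportion dying within 27 days of the start would be 1 − exp(−ln 2 × 27/152.2) = 11.6%, about 14 of 123. About 3.5%, or 4 of 123, would die on days 7 to 14.

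**Step 6: effect on a mean (assumption, for scale only).** Suppose everyone receives exactly one planned cycle and a share s dies on a day spread evenly over days 6 to 27. The average of 28/d over those days is 204.7%, so mean RDI = 100% + s × 104.7%. This gives 105%, 110% and 121% for s = 5%, 10% and 20%. With the exponential curve of step 5 and a 5-day cycle, the mean is about 112%.

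**Step 7: incomplete infusions (conditional).** Suppose one of five infusions is 90% given and that amount is recorded. Using it, (4 + 0.9)/5 = 98%. Leaving the missing dose out of the sum, 4/5 = 80%. The SAP does not say whether a missing dose is left out or makes the whole cumulative dose missing.

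**The case against.** A fair defence has several parts.

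- **The large values need special circumstances.** 200% to 400% requires death on days 7 to 14 of a one-cycle course. LoDAC and azacitidine continue over repeated cycles, so the effect is diluted. This stands.
- **The mean is not shown to exceed 100%.** A reader might infer that control-arm mean RDI will come out above plan. The documents do not support that: steps 5 and 6 assume the death shares, their timing, a single cycle and exact dosing, and any under-dosing or delay pulls the mean down. Section 7.3.1 also reports by regimen, so no pooled control mean is specified. This stands.
- **The exposure table remains usable.** A reader might conclude that adequacy of control chemotherapy can no longer be judged. That goes too far. The same table gives cumulative dose, dosing days, cycles, average daily dose, and dose decreases and interruptions, none of which truncation touches. Medians resist a few extreme values, and a maximum of 400% would draw attention.
- **Ending duration at death is proper.** It is, for the duration-of-exposure summary. It does not follow that the same duration suits dose intensity.
- **The infusion rule may be sensible.** If the form holds the prepared amount when an infusion is incomplete, setting it to missing is reasonable. The form is not shown, so this part can only be conditional.
- **Cutoff truncation is probably rare.** Version 4.0 is dated May 2022, and MEC and FLAG-IDA run for at most two cycles. This stands.

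None of this removes the defect in step 2, which follows from the SAP's formulas without any assumption about frequency.

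**Conclusion.** The point holds as a limited defect in a descriptive variable. Whenever death or cutoff falls inside the last 28-day cycle, chemotherapy dose intensity and RDI are overstated. After a full single cycle the factor is 28/d, and it falls towards 1 with more cycles or later death. The per-subject values rest only on Section 6.4; the figures for frequency and means rest on the stated assumptions and indicate scale only.

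Only the dose-intensity and RDI summaries by regimen are affected, means and maxima more than medians. OS, EFS, CR rate, error control, cumulative dose and dosing days are not affected by the truncation.

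The infusion rule is a secondary point, confined to MEC and FLAG-IDA, and it matters only if the form records the amount actually delivered. Where it applies, it lowers RDI or makes it missing, and it should not be expected to offset the inflation.

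**What to change.** 1. In Section 6.4, for chemotherapy dose intensity and RDI only, end the denominator at the initial dose date of the last cycle + 27 days, with no cut at death or cutoff. A full cycle then scores 100% whatever the day of death.
2. Keep the truncated duration for the duration-of-exposure summary.
3. Do not substitute 28 days per cycle started, because that would hide delays between cycles. Two full 5-day cycles with the second starting 14 days late give (10/70) × 28/5 = 80% under item 1, but would give 100% per cycle started.
4. For MEC and FLAG-IDA, check what the form holds when an infusion was incomplete. If it is the delivered amount, use it and set the dose to missing only when no amount was recorded. In either case, state how a missing dose enters the cumulative sum.
5. Footnote any difference from the exposure table in the primary CSR of January 2019.

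Items 1 to 3 cost SAP wording and a small program change, using dates already in the derivation. Item 4 needs no new data if the delivered amount is on the form.

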- k. For MEC and FLAG-IDA, bone marrow samples are required during screening and cycle 2 day 1. Also, an additional bone marrow sample is required at cycle 1 day 15 or later, per institutional guidelines, to assess the need for a second cycle. For LoDAC or azacitidine, bone marrow samples are required during screening, and at cycle 2 day 1 and at cycle 3 day 1. For subjects who do not achieve a CRc (CR, CRp or CRi), the bone marrow assessments will be repeated at day 1 of every 2 subsequent cycles. For subjects who achieve a CRc (CR, CRp or CRi), bone marrow sampling will be repeated at 1 month after the date of remission and every 3 subsequent cycles, or if there is suspicion of relapse in the whole blood. Bone marrow samples are also required at the end of treatment visit and as clinically indicated. If bone marrow aspirate is unobtainable (e.g., dry tap), an additional EDTA tube of peripheral blood should be collected instead. Bone marrow aspirate is required, and bone marrow biopsy is preferred. In case of inadequate aspirate, bone marrow biopsy is required.
- 1. Whole blood and buccal swab collected at day 1 for optional pharmacogenomic study.
- m. LoDAC or azacitidine dosing may continue past cycle 2.
- n. Additional clinic visits are allowed per institutional guideline for subjects receiving MEC (days 1 through 5) or FLAG-IDA (days 1 through 6). MEC and FLAG-IDA are administered for up to 2 cycles depending on response and safety assessments as described in Section 5.1 of the protocol.
- o. Chest X-ray (or CT of chest) does not need to be repeated if performed within 2 weeks prior to start of screening.
- p. For the purposes of drug preparation and dispensing activities, IRT transaction may be done prior to the visit and do not need to fall within the protocol visit window.

Footnotes continued on next page.

- q. Includes Brief Fatigue Inventory, Functional Assessment of Chronic Illness Therapy–Dyspnea-Short Forms, Functional Assessment of Cancer Therapy-Leukemia and dizziness and mouth sores items. The BFI will be administered at cycle 1 day 1 predose, cycle 1 day 8 (± 1 day), day 15 (± 1 day), cycle 2 day 1 (± 2 days), day 15 (± 1 day) and all subsequent cycles day 1 (± 2 days). Functional Assessment of Chronic Illness Therapy–Dyspnea-Short Forms, Functional Assessment of Cancer Therapy-Leukemia and dizziness and mouth sores items will be administered at cycle 1 day 1 predose, cycle 2 day 1 (± 2 days) and all subsequent cycles day 1 (± 2 days).

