- 1. Concomitant medications should be collected for reported AE/SAEs through 30 days post dose for subjects who have discontinued. For subjects who undergo HSCT, concomitant medications should be collected for reported AE/SAEs through start of conditioning treatment or 30 days post dose, whichever comes first.

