7.2.5 Previous and Concomitant Transfusions

The prior transfusions were reported in the primary CSR dated 24 JAN 2019 for the data with cutoff date of 17 SEP 2018. Only concomitant transfusions will be summarized for the end of study report.

Frequency tabulations of subjects received transfusions and blood product will be presented for previous transfusion and concomitant transfusion by treatment group Descriptive statistics will be presented for number of transfusion unit received per subject for each type of blood product.

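### Ending the concomitant medication and transfusion windows at the last dose cuts off most of the last chemotherapy cycle, so the descriptive by-arm tables are not comparable

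*SAP*

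**What the plan says.** SAP Section 6.4 gives this definition of concomitant medication: "medication with at least one dose taken between the date of first dose (inclusive) and the date of last dose (inclusive) of study drug". The transfusion definition in the same section reads: "Concomitant transfusion is defined as transfusion received between the date of first dose (inclusive) and the date of last dose (inclusive) of study drug". Neither definition extends past the last dose. The only special case is the gap around an on-study transplant for subjects who plan to resume ASP2215.

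The same section uses a different end date for exposure. For ASP2215 it is the last dose date. For chemotherapy the rule reads: "For chemotherapy, last date of exposure = (initial dose date of the last cycle +28-1) or death date if death occur within last cycle".

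Section 7.2.4 tabulates concomitant medications by treatment group on the safety set. Section 7.2.5 tabulates concomitant transfusions by treatment group and adds: "Descriptive statistics will be presented for number of transfusion unit received per subject for each type of blood product". Neither section states an adjustment for time on treatment. Both keep the concomitant tables, but not the prior ones, for the end-of-study report.

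Two other windows run longer. Section 6.2 counts adverse events as treatment-emergent if they begin within 30 days after the last dose. Table 3, footnote l, says: "Concomitant medications should be collected for reported AE/SAEs through 30 days post dose for subjects who have discontinued".

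**The concern.** For a daily oral drug, the last dose is close to the end of treatment. For a regimen given over a few days of a 28-day cycle, it is not. Section 6.4 allows for this when it computes exposure but not when it defines concomitant use.

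Take, as an illustration, a subject given one cycle of MEC who is transfused, or started on a new drug, on day 12. The event being treated counts as treatment-emergent. The transfusion or drug does not count as concomitant.

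The comparability of the by-arm tables of supportive care is at stake. Relative to each arm's exposure period the loss falls on the chemotherapy arm, so ASP2215 may look relatively more transfusion- and medication-intensive than it is.

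**Working it through.** **Inputs**

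- Cycle length: 28 days (Section 3.2.1).
- Dosing days per cycle: Table 2, footnote n, allows additional visits for subjects "receiving MEC (days 1 through 5) or FLAG-IDA (days 1 through 6". I take 5 days for MEC and 6 for FLAG-IDA. The planned dose intensity in Section 6.4 uses at most 5 days for any FLAG-IDA component, so 5 is possible there too. The same list gives 7 days for azacitidine and 10 for LoDAC.
- Number of cycles: one for MEC or FLAG-IDA, with a second in some subjects. LoDAC and azacitidine continue until a discontinuation criterion is met (Section 3.2.1).
- ASP2215: daily (Table 1, footnote n).

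**Formulas**, with cycles starting on schedule (days 1, 29, and so on):

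- Counted days = 28 × (cycles − 1) + dosing days in the last cycle.
- Exposure days = 28 × cycles.

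**The plan's own figure first.** For a one-cycle chemotherapy subject, the last date of exposure is day 1 + 27 = day 28, and the duration is 28 − 1 + 1 = 28 days. This agrees with the formula.

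**Results**

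| Regimen | Cycles | Counted days | Exposure days | Share |
|---|---|---|---|---|
| MEC | 1 | 5 | 28 | 18% |
| FLAG-IDA | 1 | 6 (or 5) | 28 | 21% (or 18%) |
| Azacitidine | 1 | 7 | 28 | 25% |
| LoDAC | 1 | 10 | 28 | 36% |
| MEC | 2 | 28 + 5 = 33 | 56 | 59% |
| FLAG-IDA | 2 | 28 + 6 = 34 | 56 | 61% |
| Azacitidine | 4 | 84 + 7 = 91 | 112 | 81% |
| LoDAC | 4 | 84 + 10 = 94 | 112 | 84% |
| ASP2215 | 1, 2 or 4 | 28, 56 or 112 | 28, 56 or 112 | 100% |

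**Against the treatment-emergent window.** For one-cycle MEC this runs to day 5 + 30 = 35, and the concomitant rule omits 30 of 35 days (86%). For four cycles of ASP2215 it runs to day 112 + 30 = 142, and the rule omits 30 of 142 days (21%). Both arms lose the tail, but very unequally.

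**Effect of the change.** With the last date of exposure as the end, one-cycle MEC or FLAG-IDA subjects are counted for 28 days instead of 5-6. ASP2215 is unchanged. A four-cycle ASP2215 subject still contributes 112 days against 28, so unadjusted units per subject would remain unequal in follow-up.

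**Are the data there?** Table 2 schedules concomitant medication recording at days 8 and 15 of cycle 1, after MEC and FLAG-IDA dosing has ended. Day 28 also lies within 30 days of a day-5 last dose (day 35), although after discontinuation only medications for reported adverse events are collected. The SAP does not say how long transfusions are recorded after the last dose.

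**The case against.** The strongest reply is that the tables follow a stated definition, are descriptive and carry no test. They sit under Study Population, and Section 6.2 lists neither medications nor transfusions among the safety variables. This stands. A reader might infer that the tables would be wrong; the document supports only that they are not comparable between arms.

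Section 7.4.4 separately tests resource use, including blood transfusion, over the entire study period with no cut at last dose. This also stands, but it does not repair Section 7.2.5. It addresses the incidence of transfusion and not units, and it sits under the efficacy analyses that Section 7.4 says are not performed for the end-of-study report.

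A reader might infer that only the chemotherapy arm loses time. That is true against the exposure period. Against the treatment-emergent window, ASP2215 subjects also lose 30 days.

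A reader might also take the day shares as shares of records lost. They are not. A medication counts if a single dose falls in the window, so anything begun before or during dosing is kept. For transfusions, a share of days equals a share of units only if the rate is constant, which the SAP does not establish.

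Finally, Section 8 records that version 3.0 clarified this end date, so it was considered. The entry does not mention intermittent dosing. The version 2.0 entry gives unsuitability for chemotherapy as the reason for revising the exposure variables, and the concomitant definitions do not carry the same correction.

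**Conclusion.** The point holds as a comparability defect in retained descriptive tables. The counted share of exposure is smallest for one-cycle high-intensity subjects and rises with each further cycle. The undercount on chemotherapy falls mainly on transfusions and on medications first started after dosing ends.

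The effect on the whole arm cannot be computed, because the SAP gives neither the distribution of regimens and cycles nor the timing of transfusions. The day counts assume that cycles start on schedule and that the last dose date is read literally, as a term separate from the last date of exposure.

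No efficacy endpoint, hypothesis test or error rate is affected. The transfusion conversion and maintenance rates are defined for ASP2215 only, with their own periods, and are unaffected. The change is worth making before the end-of-study tables are produced, but the trial's conclusions do not depend on it.

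**What to change.** In both concomitant definitions in Section 6.4, for chemotherapy subjects, replace the last dose date with the last date of exposure that the section already defines: first dose of the last cycle + 27 days, or death or data cutoff if earlier. Keep the last dose for ASP2215. Use the same end date for transfusion units per subject in Section 7.2.5.

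Also present transfusion units per patient-time of exposure, since the new end date does not equalise follow-up. Section 7.5.1 already adjusts adverse event counts by patient-years of drug exposure, so the approach is not new to the plan.

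The cost is a short amendment to Section 6.4, a line in Section 7.2.5 for the rate, and a re-run of two table sets. The downside is that chemotherapy-arm counts will differ from those in the primary CSR, so the changed window should be footnoted. Before the change is adopted, confirm from the CRF that transfusions after the last dose were captured; if they were not, the transfusion table should state that limit.
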